5.3.1.1.2 Ophthalmologic Examinations

Although ophthalmic evaluation for ROP is usual care, special attention to these examinations is required because they are central to the primary outcome, and a confirming examination is required for severe ROP. Confirming exams are not universally conducted in usual care.

Type 1 ROP, as defined by the ETROP multicenter study (2003) is the current minimal degree of severity of ROP found to warrant intervention (laser, cryotherapy or other approaches to control accelerating retinal neovascularization). Moderate ROP that does not fully meet these criteria (now termed "Type 2" ROP) had better outcomes when left to its natural course (52% spontaneously resolved) or treated when/if it reached Type 1 criteria, as compared to when it was treated at the level of Type 2 ROP (ETROP 2011)(Repka 2011). Therefore since Type 2 ROP does not have the same prognostic clinical importance as Type 1 (except as a warning to watch closely), the criteria for warranting intervention (Type 1) was chosen as the adverse endpoint for this study.

Each center will have at least 1 study-certified ophthalmologist who is the Lead Ophthalmologist for that center. This physician is a co-investigator on the study, has read the protocol and serves as the spokesperson and coordinates communication with other ophthalmologists performing examinations or treating ROP in the NICU and as outpatients at that Center. All ophthalmologists participating in ROP examinations in the community (varies from 1 to several) will be informed about the INS-3 protocol, and the one to one relationship of our study practices to recommended practice including: timing of first and repeat examinations, recording of examination findings using the International Classification of ROP (ICROP 2006) conventions, and the criteria for intervention for ROP (Early Treatment for Retinopathy of Prematurity [ETROP] Type 1) (ETROP Study Group 2003) (2013 Guidelines for Perinatal Care)(2013 AAP/AAO/AAPOS Screening examination of premature infants for ROP).

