or the vessels have unequivocally reached Zone III on one examination in an infant of 35 weeks PMA or older, if there has been no previous ROP in Zone I or Zone II, and this examination is not the only examination the infant has had.

or PMA has reached 50 weeks and there is no prethreshold or worse ROP present.

Prethreshold ROP =

in Zone II, Stage 3 ROP or

in Zone I, any stage ROP

Unfavorable Acute/Final ROP Status: when one or both eyes show any of the following findings/circumstances, confirmed by a second examiner (or documented by fundus photograph):

ETROP Type 1 ROP (see above)

ROP that has progressed to stages worse than ETROP Type 1 ROP, including classic CRYO-ROP threshold, or any degree of retinal detachment;

Note: MISSING OUTCOME: If an infant receives an intervention for ROP before meeting criteria for an Unfavorable outcome or does not have a confirming examination (or fundus photographs), the infant's outcome will be considered a missing outcome. Intervening prior to this point is a study protocol violation and will require completion of a Protocol violation form by the treating physician explaining the circumstances. Handling of missing and indeterminate outcomes for the publication and regulatory submission analyses are discussed in Section 8.1.4.

An infant who dies before reaching a favorable Acute/Final ROP status will be considered to have an unfavorable Acute/Final ROP outcome, since death is a competing outcome for severe ROP (Freemantle 2003).

For infants who reach an unfavorable ROP status, a confirmatory examination is the preferred approach for validating the outcome, (but if such an examination cannot be performed, fundus photography for later evaluation is required). Infants that receive intervention without a confirming examination (or photographs) will be categorized as having a missing outcome. The confirming examiner is normally the retinal surgeon who will perform the intervention, and must

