8.1.2 Data Sets Analyzed

Depending on type, each analysis will be conducted within one or more of the following analysis populations. For the overall study analyses for publication, each population will include all infants that meet the population definition. For the regulatory submission analyses conducted within regulatory sub-studies, each sub-study will have a set of analysis populations per the definitions below that only comprise the infants assigned to that regulatory sub-study.

The safety population will include all infants who were randomized and received at least 1 dose of study drug. The safety population will be used for all safety analyses and infants will be grouped according to actual treatment received.

The ITT population is the primary population for formal efficacy analyses. This population includes all subjects randomized. For these analyses, subjects will be analyzed as part of the study arm to which they are assigned by randomization, regardless of the actual therapy they received.

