8.1.4 Efficacy Analyses

For scientific publication, Robust Poisson regression adjusting for center and GA strata will be used to estimate adjusted relative risk (and associated 95% CI) for myo-Inositol 5% Injection vs. placebo. The primary hypothesis will be tested based on a score test of the treatment effect in the Poisson regression model where the null hypothesis of no treatment effect on survival without severe ROP is rejected at either the interim or final analysis with a p-value consistent with an overall Type 1 error rate of 0.05 and a Bonferroni-type correction for multiple comparisons. (Casella and Berger 2002) For this analysis, individuals with indeterminate primary outcome status (i.e. alive through 55 weeks PMA and did not meet final acute ROP status but have ROP assessment data available), will go through an endpoint adjudication process and the resulting adjudicated endpoints will be used in the analyses. Individuals with completely missing outcomes (i.e. no ROP follow-up or death information available) or for which an adjudicated endpoint cannot be determined will be excluded from the analyses.

The following analyses will be conducted for a regulatory submission, provided there is evidence of efficacy. As suggested by the FDA, the primary outcome will be treated as a three level ordinal endpoint where the unfavorable outcomes are assigned a value of -1, indeterminate outcomes are assigned a value of 0, and favorable outcomes are assigned a value of +1. No adjudicated outcomes will be used.

The outcomes will be displayed in the following table:

Table 8. Outcomes Display of all enrolled subjects for the Regulatory Analysis

Outcome Status	Placebo (N1)	Inositol (N2)	Difference
Favorable (1)	n11 (n11/N1)	n21 (n21/N2)	XX
Unfavorable (-1)	n12 (n12/N1)	n22 (n22/N2)	XX
Indeterminate (0)	n13 (n13/N1)	n23 (n23/N2)	XX
Missing (by multiple imputation)	n14 (n14/N1)	n24 (n24/N2)	XX

This endpoint will be analyzed using a 2-sided Mantel-Haenszel chi-square test using modified ridit scores for ordinal data controlling for strata defined by study center and gestational age with

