the analyses being completed separately within each of the two regulatory sub-studies. Individuals with completely missing outcomes (i.e. no ROP follow-up or death information available) will be imputed using a multivariate technique for multiple imputation. Formal inference based on the regulatory analyses is conditional on the findings of the primary analysis for scientific publication demonstrating a benefit (i.e. null hypothesis rejected at either the interim or final analysis with a p-value consistent with an overall Type 1 error rate of 0.05 and Bonferroni-type correction for multiple comparisons). This prioritization of analyses precludes the necessity of adjusting alpha for the additional regulatory analyses.

Various sensitivity analyses for both publication and regulatory submission will be performed to assess the impact of missing/indeterminate outcomes and robustness of the finding across multiple clinically relevant subpopulations. For example, if the results of the primary publication analysis of this multi-center trial are positive, then sensitivity analyses of the primary outcome will be performed to examine internal consistency of the study results. Specifically, consistency of treatment effect across subsets defined by GA strata and center separately will be assessed using the robust Poisson regression model. For GA strata, an interaction between GA strata and treatment will be added to the model. A p-value for the interaction >0.2 will be indicative of no interaction effect. If heterogeneity of treatment effect is present, then the likelihood ratio test (Gail and Simon 1985) will be used to determine whether the interactions are qualitative in nature (i.e., a test of the null hypothesis that inositol is at least as good as placebo in every subset of subjects vs. the alternative hypothesis that a cross-over effect exists such that placebo outperforms inositol in at least 1 of the subset of subjects). This same approach will also be used to assess consistency of treatment effect across centers. However, to ensure adequate power for identifying qualitative interactions among centers, the consistency analyses will be conducted with centers clustered into 4 subgroups defined by baseline prevalence of unfavorable ROP status (high vs. low) and expected enrollment size (large vs. small).

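### Infants treated for ROP without confirmation, or before criteria are met, are called missing in Section 5.3.1.1.2, but Section 8.1.4 has no class that fits them

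*Protocol*

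**What the plan says.** Section 5.3.1.1.2 (Ophthalmologic Examinations) accepts an unfavorable status only when it is "confirmed by a second examiner (or documented by fundus photograph"). Two groups of treated infants are then given a missing outcome:

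- those treated without confirmation: "Infants that receive intervention without a confirming examination (or photographs) will be categorized as having a missing outcome";
- those treated early: "If an infant receives an intervention for ROP before meeting criteria for an Unfavorable outcome". This is also a protocol violation.

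The section continues: "Handling of missing and indeterminate outcomes for the publication and regulatory submission analyses are discussed in Section 8.1.4".

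Section 8.1.4 (Efficacy Analyses) defines two classes without an observed outcome.

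- *Indeterminate*: alive through 55 weeks PMA, final acute status not met, ROP assessment data available. These infants are adjudicated for publication and scored 0 in the regulatory analysis, which uses no adjudicated outcomes.
- *Completely missing*: no ROP follow-up or death information. For publication these infants, and those "or for which an adjudicated endpoint cannot be determined will be excluded from the analyses". For the regulatory analysis: "Individuals with completely missing outcomes (i.e. no ROP follow-up or death information available) will be imputed using a multivariate technique for multiple imputation".

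Section 8.1.2 says of the ITT population, the primary one for efficacy: "This population includes all subjects randomized". Section 8.2 allows 3-5% non-evaluable infants and describes them only as lost to follow-up.

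**The concern.** An infant who was examined, judged to have Type 1 ROP and treated has eye data on the CRF. That infant is not completely missing as Section 8.1.4 defines it, yet Section 5.3.1.1.2 calls the outcome missing. Two analysts could code the same infant differently on the primary endpoint.

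The class is also tied to the outcome, because only infants judged to need treatment can enter it. Section 8.1.4 justifies its handling of incomplete follow-up by saying that such infants are mostly improving. That argument does not carry over to infants who were treated. If they are dropped, more are lost from the arm with more severe ROP. The risk difference shrinks, and the sample-size allowance does not count the loss.

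**Working it through.** **1. Place the infant in each class.** Take an infant with Type 1 ROP recorded by the first examiner, treated, with no second examination or photographs, alive at 55 weeks PMA.

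| Reading | Publication analysis | Regulatory analysis |
|---|---|---|
| Missing (label in 5.3.1.1.2) | excluded | multiply imputed |
| Indeterminate (wording of 8.1.4) | adjudicated; excluded if unresolved | scored 0 |

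The missing reading contradicts the definition in 8.1.4, and the indeterminate reading contradicts the label in 5.3.1.1.2. On neither reading does the recorded finding itself produce -1 in the regulatory analysis.

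**2. Reproduce the plan's sample size.** Section 8.2 gives 0.30 against 0.23, two-sided alpha 0.05 and 90% power. The pooled two-proportion formula without continuity correction gives 834 per arm, 1668 in total, against 1672 stated. Power at 836 per arm is 0.901. With 5% loss, 1672/0.95 = 1760, as stated.

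**3. Effect of dropping these infants.** Inputs:

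- 836 per arm (Section 8.2); alpha 0.0499 at the final analysis (Section 8.1.5).
- Placebo death 0.18 (Table 9, all-cause death). Severe ROP 0.30 - 0.18 = 0.12. This split is an assumption.
- Inositol, effect on ROP only: death 0.18, severe ROP 0.05. Inositol, proportional effect: 0.138 and 0.092. Both total 0.23.
- q, the share of severe-ROP infants treated without confirmation and dropped. The protocol gives no value, so q is varied.

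Observed rate per arm: p = (death + sROP × (1 - q)) / (1 - sROP × q), with n = 836 × (1 - sROP × q).

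Example, placebo, q = 0.10: p = (0.18 + 0.108)/(1 - 0.012) = 0.288/0.988 = 0.2915. Inositol, ROP only: (0.18 + 0.045)/(1 - 0.005) = 0.225/0.995 = 0.2261. The difference is 0.0654.

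| q | ROP only: difference | power | infants dropped | Proportional: difference | power | infants dropped |
|---|---|---|---|---|---|---|
| 0 | 0.070 | 0.90 | 0 | 0.070 | 0.90 | 0 |
| 5% | 0.068 | 0.88 | 7 | 0.069 | 0.90 | 9 |
| 10% | 0.065 | 0.86 | 14 | 0.069 | 0.89 | 18 |
| 20% | 0.061 | 0.81 | 28 | 0.067 | 0.88 | 35 |
| 30% | 0.056 | 0.74 | 43 | 0.066 | 0.87 | 53 |

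The publication analysis reports a relative risk, truly 0.23/0.30 = 0.767. At q = 10% it becomes 0.2261/0.2915 = 0.776 if the effect is on ROP only, which is toward 1. It becomes 0.2229/0.2915 = 0.765 if proportional, which is essentially unchanged. The shrinkage toward zero in every row is therefore a statement about the risk difference.

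**The case against.** The case that this matters little is substantial.

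- **Exclusion is not settled.** Read literally, Section 8.1.4 lets a surviving treated infant be adjudicated for publication, possibly as unfavorable, and excluded only if that fails. This stands: the conflict between sections is certain, and the exclusion is one reading of it.
- **Numbers should be small.** The sentence "Confirming exams are not universally conducted in usual care" explains why the study requires confirmation. The treating surgeon's recorded examination normally counts, and fundus photographs are an accepted substitute. In INS-2 (Table 6) the composite was undetermined before adjudication in 2 + 1 + 0 + 4 = 7 of 122 infants, and in 1 afterwards. This stands too: the lower rows of the table have no support in the documents.
- **Early-treated infants are not proven events.** A reader might infer that every infant in this class is a lost unfavorable outcome. For those treated before Type 1 was recorded, the endpoint had not been met and the untreated course cannot be seen. That is an intercurrent-event question.
- **Imputation need not favor a good outcome.** A reader might infer that imputation would return mostly favorable values. The protocol does not specify the imputation model, so no such figure can be given.
- **Sensitivity analyses are planned.** Section 8.1.4 foresees them for missing and indeterminate outcomes. They do not settle the primary coding.

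Masking makes unequal loss by arm for reasons other than the outcome unlikely. The general complaint that exclusion departs from ITT applies to any missing outcome and adds little here.

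**Conclusion.** The point holds as a coding conflict on the primary endpoint that should be fixed. Sections 5.3.1.1.2 and 8.1.4 disagree on the class of a treated, unconfirmed infant, and the regulatory analysis has no route by which a recorded and treated Type 1 finding scores -1 as observed.

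The likely size is modest. With 5-10% of severe-ROP infants affected and dropped, power falls from 90% to about 86-88% if the effect lies wholly on ROP, or stays at 89-90% if it is proportional. Shares of 20-30% would give 74-81% or 87-88%, but these are upper bounds without documentary support. All of these figures rest on the assumed 0.18/0.12 split, on an assumed q that is equal in both arms, and on the reading under which the infants are dropped. The documents do not show that the situation will be common or that the trial's conclusion is at risk.

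**What to change.** Reconcile Section 5.3.1.1.2 with Section 8.1.4 before unmasking. The change concerns outcome coding only.

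1. Give treated infants an explicit class in Section 8.1.4.
2. Count Type 1 or worse recorded by the first examiner and followed by treatment, with no confirmation or photographs, as unfavorable: an event for publication and -1 in the regulatory analysis. Align the Synopsis and Section 5.3.1.1.2, which now make a second evaluation part of the definition.
3. Send infants treated before Type 1 was recorded to the endpoint adjudication already planned for publication, done masked. State their regulatory score in advance, since that analysis uses no adjudicated outcomes.
4. Show the alternative codings (unfavorable, indeterminate, missing as now) as sensitivity analyses. Defaulting unresolved early-treated infants to unfavorable is debatable and belongs here.
5. Reserve the missing label for infants with no ROP and no vital-status data.

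The cost is wording in the protocol and in any SAP. The downside is that a few unconfirmed Type 1 calls may be false positives; under masking these should be non-differential.

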5.3.2 Efficacy Variables

5.3.2.1 Primary Variable

The primary outcome is survival without severe ROP through Acute/Final ROP status determination (favorable) versus development of severe ROP or death prior to reaching Acute/Final ROP status (unfavorable) followed up to 55 weeks PMA.

- Death in relation to the primary variable will be defined as from any cause before Acute/Final ROP status is determined.
- Favorable Acute/Final ROP status is defined in the above section and requires that no ROP, or only mild ROP has occurred in both eyes and that the eyes have matured beyond the risk of developing severe ROP.

- Unfavorable ROP is defined in the section above and requires that one or both eyes reach ROP severity warranting intervention.

5.3.2.2 Secondary Variables

- BPD: NICHD Physiologic Definition: Requiring oxygen to maintain an oxygen saturation of at least 90% at 36 weeks PMA (Walsh 2004).
- BPD (Physiologic Definition) or Death from BPD prior to 37 weeks PMA, with cause of death certified by the Center PI that BPD is the primary cause, or a significant co-contributing cause of death.
- All cause death: defined as death from any cause following randomization. The primary, underlying cause of death will be certified by the Principal Investigator at each center who may also list co-contributing causes.
- Any ROP: defined as ROP of any severity that is observed on at least 2 examinations in either eye through the time that Acute/Final ROP status is reached. ROP that is observed on only 1 of multiple eye examinations will not be considered “any ROP”. An infant who has only 1 eye examination prior to death, and that examination shows any stage ROP, will be also be considered as having “any ROP”.
- Type 2 ROP through the time that Acute/Final ROP status is reached: defined as 1 or both eyes reaching Type 2 ROP (ETROP 2003), but not Type 1. Type 2 ROP is defined as: (ETROP 2003).
 - in Zone II: Stage 3 ROP without Plus Disease, or
 - in Zone I: Stage 1 or 2 ROP without Plus Disease
- Severe IVH: IVH Grades 3 or 4 on either side of the brain, or extensive PVL. IVH will be classified as described by Papile (Papile 1978). PVL will be graded by the characteristics of the periventricular white matter on ultrasound or MRI done between 4 to approximately 6 weeks after birth per usual care (Barkovich 2000) and/or porencephalic cyst.

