Due to the declining serum levels as the infants matured, it was not possible to estimate a population pharmacokinetic model from the serum levels collected after initiation of enteral administration. However, a multiple-dose version of the same modified one-compartment model used with the INS-1 study was compatible with the serum levels measured during IV administration. For a typical infant, the volume of distribution (676.7 mL/kg) and clearance (57.6 mL/kg/hr) were similar to those measured in INS-1. Estimates for the half-life (8.1 hr) and endogenous "concentration" (41.4 mg/L), were also comparable to the INS-1 estimates.

Table 6. Clinical Outcomes through Discharge or 120 Days (INS-2; Preliminary Unpublished Data)

Characteristic	Placebo (N=35)	Inositol			P-value across groups	NRN 2008-2009 ^d (N=1415)
		10 mg/kg/d (N=29)	40 mg/kg/d (N=30)	80 mg/kg/d (N= 28)		
Gestational age, weeks, mean (SD)	26.5 (0.3)	26.6 (0.3)	26.7(0.3)	26.7 (0.4)		
Birth weight, grams, mean (SD)	884 (38)	897 (50)	939 (45)	920 (54)		
Died	6 (17%)	2 (7%)	6 (20%)	1 (4%)	0.165	162 (11%)
BPD (O2 @ 36 weeks) ^a	11 (38%)	7 (26%)	7 (30%)	8 (30%)	0.814	465 (38%)
Death from BPD before 37 weeks, or BPD	11 (38%)	8 (29%)	7 (30%)	8 (30%)	0.880	
PDA	13 (37%)	14 (48%)	14 (47%)	10 (36%)	0.677	615 (43%)
if PDA, indomethacin or ibuprofen	8 (77%)	9 (31%)	8 (27%)	8 (29%)	0.902	407 (29%)
If PDA, surgical ligation	3 (9%)	3 (10%)	1 (3%)	3 (11%)	0.745	152 (11%)
IVH grade any	13 (38%)	4 (14%)	10 (34%)	5 (18%)	0.078	405 (29%)
IVH Grade III or IV	10 (29%)	2 (7%)	6 (21%)	2 (7%)	0.052	233 (16%)
Sepsis, late onset	4 (11%)	6 (21%)	7 (23%)	5 (18%)	0.627	310 (22%)
NEC suspected or proven	5 (14%)	1 (3%)	4 (13%)	1 (4%)	0.281	125 (9%)
NEC requiring surgery	3 (9%)	0	2 (7%)	0	0.170	64 (5%)
Spontaneous GI perforation without NEC	2 (6%)	0	2 (7%)	1 (4%)	0.721	64 (5%)
Hearing screening test, failed in either ear	1 (4%)	1 (4%)	4 (20%)	3 (14%)	0.255	131 (12%)
ROP outcomes: all subjects (N) ^b	(35)	(29)	(30)	(28)		
Severe ROP in at least 1 eye	5/27 (19%)	3/26 (12%)	2/24 (8%)	2/23 (9%)	0.717	
Severe ROP in at least 1 eye or death before final/acute ROP status	11/33 (33%)	5/28 (18%)	8/30 (27%)	3/24 (13%)	0.274	
^c Adjudicated: Severe ROP in at least 1 eye, or death prior to final/acute status.	11/35 (31%)	5/29 (17%)	8/30 (27%)	3/27 (11%)	0.227	
ROP outcomes: In Target population of 23- 27 weeks (N)	(N=27)	(N=23)	(N=22)	(N=20)		
Severe ROP in at least 1 eye	5/19 (26%)	3/20 (15%)	2/16 (13%)	2/15 (13%)	0.762	

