Although the study is only powered to formally test one primary hypothesis of efficacy (treatment effect on survival without sROP), a variety of secondary outcomes will be assessed in an exploratory manner. Due to the exploratory nature of these secondary analyses, no additional adjustments for multiplicity outside of accounting for the interim analysis are planned. Given a sample size of 1760 (effective sample size of 1672 infants), the probabilities of detecting a potential treatment effect (i.e., 30% reduction or increase) for the overall study population in common clinical outcomes of secondary interest are summarized in Table 9.

Table 9. Probabilities of Detecting Potential Treatment Effect on Secondary Outcomes

	Underlying Prevalence	Absolute Effect for 30% Change	Probability of Detecting	
			Reduction	Increase
Death all cause	0.18	0.054	0.87	0.78
BPD physiologic definition	0.38	0.114	0.99	0.99
BPD or death from BPD before 37 weeks PMA	0.49	0.147	1.00	1.00
Any ROP	0.65	0.195	1.00	1.00
Type 2 ROP	0.25	0.075	0.96	0.92
Severe IVH (Grade III/IV or shunt or PVL)	0.20	0.060	0.90	0.83

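### The composite of BPD or death from BPD leaves deaths from other causes unplaced, and its 0.49 planning rate very probably belongs to BPD or death from any cause

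*Protocol*

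**What the plan says.** Protocol section 5.3.2.2 lists BPD alone as a secondary outcome, defined as "Requiring oxygen to maintain an oxygen saturation of at least 90% at 36 weeks PMA". It then lists the composite: "BPD (Physiologic Definition) or Death from BPD prior to 37 weeks PMA, with cause of death certified by the Center PI" as the primary or a significant co-contributing cause. All-cause death is a separate secondary outcome.

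Table 9 in section 8.2 gives planning rates and power for a 30% change at an effective sample size of 1672. The composite's row reads "BPD or death from BPD before 37 weeks PMA 0.49 0.147 1.00 1.00"; the columns are prevalence, absolute change, and power for a reduction and for an increase. The same table puts BPD alone at 0.38 (power 0.99 in both directions) and all-cause death at 0.18 (power 0.87 for a reduction, 0.78 for an increase).

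Section 8.2 calls the secondary analyses exploratory. Section 8.1.2 makes all randomized infants the primary efficacy population.

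Table 6 (INS-2) holds the only tabulated example of this composite, in the row "Death from BPD before 37 weeks, or BPD": 11 (38%) on placebo, then 8 (29%), 7 (30%) and 8 (30%) on 10, 40 and 80 mg/kg/day.

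**The concern.** Any death before 36 weeks PMA prevents the BPD assessment, whatever its cause, but only deaths certified as due to BPD count as events. The rest must go somewhere, and the INS-3 protocol does not say where. If they leave the denominator, the arms are compared in groups selected by survival after randomization. If they stay as non-events, infants who died are scored as free of BPD.

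This matters because the protocol's own evidence points to an effect on mortality: the meta-analysis in Table 4 gives a risk difference for death of -0.131. For the primary outcome the protocol deals with the same problem by counting death from any cause (sections 5.3.1.1.2 and 5.3.2.1). The earlier evidence also counts all deaths: Tables 1 and 2 report survival without BPD, and Table 4 reports death or BPD. The INS-3 composite departs from both without a stated reason.

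The 0.49 also looks too high for the labelled outcome. It exceeds the BPD rate by 0.11, while in INS-2 adding BPD deaths to BPD added one infant in one group.

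**Working it through.** **1. Reproducing Table 9.** Inputs: 836 per arm (1672/2), two-sided alpha 0.05 (assumed to carry over from the primary test), p against 0.7p or 1.3p. With p1 and p2 the two rates and p their mean,

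z = [|p1 − p2| − 1.96·√(2p(1−p)/n)] / √([p1(1−p1) + p2(1−p2)]/n), power = Φ(z).

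- All-cause death: 0.867 / 0.778 (printed 0.87 / 0.78).
- Type 2 ROP: 0.964 / 0.924 (printed 0.96 / 0.92).
- Severe IVH: 0.905 / 0.831 (printed 0.90 / 0.83).
- Composite at 0.49: 1.000 / 1.000 (printed 1.00 / 1.00).
- BPD at 0.38: 0.9988 / 0.9971, which would round to 1.00; printed 0.99 / 0.99. With survivors only (0.82 × 836 ≈ 685 per arm) it is 0.9949 / 0.9895, which does round to 0.99 / 0.99. This suggests that 0.38 is a rate among survivors.

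**2. INS-2 denominators.** For each printed count, only one denominator gives the printed percentage:

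| Group | Randomized | Died | BPD | Composite |
|---|---|---|---|---|
| Placebo | 35 | 6 | 11/29 | 11/29 |
| 10 mg/kg/day | 29 | 2 | 7/27 | 8/28 |
| 40 mg/kg/day | 30 | 6 | 7/23 | 7/23 |
| 80 mg/kg/day | 28 | 1 | 8/27 | 8/27 |

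Placebo 29 is 35 − 6, and 80 mg/kg/day 27 is 28 − 1. In the 10 mg/kg/day group one death returns as an event and the other stays out. The 40 mg/kg/day denominator is one below 30 − 6 = 24, without explanation. So INS-2 dropped deaths from other causes, and about 1 of its 15 deaths entered as a BPD death.

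**3. What 0.49 matches.**

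- BPD or any death: 0.18 + (1 − 0.18) × 0.38 = 0.18 + 0.3116 = 0.4916.
- INS-2 placebo, BPD or any death: (11 + 6)/35 = 48.6%, assuming no infant is counted twice. The composite as labelled is 38%.

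Let d be the rate of BPD deaths. The d needed for the labelled outcome to reach 0.49 is:

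- Other deaths excluded: (0.3116 + d)/(0.82 + d) = 0.49, so d = 0.1769, or 98% of all deaths.
- Other deaths as non-events: d = 0.49 − 0.3116 = 0.1784, or 99%.
- If 0.38 were a rate among all randomized infants: d = 0.49 − 0.38 = 0.11, or 61%.

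**4. Rate and power for the labelled outcome.** With a share s of deaths due to BPD, d = 0.18s. The rate is (0.3116 + d)/(0.82 + d) with other deaths excluded, or 0.3116 + d with them as non-events.

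| s | Excluded | Non-events |
|---|---|---|
| 1/15 (INS-2) | 0.389 | 0.324 |
| 10% | 0.393 | 0.330 |
| 50% | 0.441 | 0.402 |

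At s = 1/15, power is 0.996 / 0.993 (about 696 per arm) or 0.994 / 0.985 (836 per arm). Even with no BPD deaths, the lowest value is 0.979.

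**5. What a mortality effect does.** Take the plan's own 30% reduction in death, 0.18 to 0.126. Let the extra 0.054 survivors have BPD risk r, and let a fraction a of the averted deaths be ones that would have been certified as BPD deaths; assume no other death is. With r = 0.80 (assumed):

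- Other deaths excluded. Inositol: (0.3116 + 0.054 × 0.80)/0.874 = 0.406. Placebo: (0.3116 + 0.054a)/(0.82 + 0.054a), which is 0.380 at a = 0 and 0.418 at a = 1. Inositol looks 2.6 points worse or 1.2 points better; the arms are equal at a ≈ 0.66.
- Other deaths as non-events. Inositol: 0.3116 + 0.0432 = 0.355. Placebo: 0.3116 + 0.054a, which is 0.312 at a = 0 and 0.366 at a = 1. Inositol looks 4.3 points worse or 1.1 points better; the arms are equal at a = r = 0.80.
- BPD or any death: 0.492 on placebo, 0.126 + 0.3548 = 0.481 on inositol.

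At a = 0, with r from 0.38 to 0.90, the apparent harm is 0 to 3.2 points (excluded) or 2.1 to 4.9 points (non-events). Over that range, BPD or any death stays lower on inositol, at 0.458 to 0.486.

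**The case against.** A lung-specific composite is a legitimate choice, and the protocol names it consistently in the synopsis, section 5.3.2.2 and Table 9. The outcome is exploratory. All-cause death is reported beside it and any-cause death is part of the primary outcome, so a shift in mortality would be visible. Certifying investigators are masked (section 5.5.5), so errors of attribution should not favour an arm through knowledge of assignment. With about 700 per arm and a rate near 0.39, the standard error of a difference is √(2 × 0.39 × 0.61/700) ≈ 2.6 points, the size of the illustrated distortion with other deaths excluded. All of this stands and limits the weight of the point.

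INS-2 is also an imperfect guide. It enrolled 23 to 29 weeks, its BPD row is not labelled physiologic, its composite row does not mention co-contributing causes, and its data are marked preliminary. Its 1 in 15 may understate the share in INS-3.

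Three stronger readings are not supported:

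- A reader might infer that the composite must make inositol look harmful if it saves lives and protective if it costs lives. That follows for BPD among survivors when the infants whose survival changes have above-average BPD risk. For this composite the direction depends on attribution, as step 5 shows.
- A reader might infer that INS-3 will drop deaths from other causes. The protocol does not say so; only INS-2 practice points that way, and the SAP is not at hand.
- A reader might take the match to 0.49 as exact, or the labelled outcome as unable to reach it. The value is 0.4916, the source of 0.49 is not given, and on one reading of 0.38 a 61% share of BPD deaths would suffice.

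**Conclusion.** The point holds in a limited form. The composite omits deaths that preclude BPD assessment, and the protocol does not place them. Excluding them selects on survival; keeping them as non-events scores infants who died as BPD-free. In the illustration the apparent effect runs from 4.3 points against inositol to 1.2 points in its favour, depending on the denominator and on attribution.

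The 0.49 very probably belongs to BPD or death from any cause. This rests on two agreeing routes (0.4916 and 48.6%), on reading 0.38 as a rate among survivors, and on treating the whole 0.18 as deaths before assessment. The labelled outcome would be about 0.39 or 0.32 on INS-2's share of BPD deaths, and about 0.33 to 0.44 if 10 to 50% of deaths are BPD deaths.

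The sample size is unaffected, since power stays at about 0.98 or more. What is at stake is how a secondary result can be interpreted and compared with the earlier trials. The change is worth making but is not critical.

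**What to change.** Make the BPD composite physiologic BPD at 36 weeks PMA or death from any cause before that assessment, analysed in all randomized infants, and attach the 0.49 in Table 9 to it. Keep the cause-specific composite as a supportive outcome, state whether deaths from other causes are excluded or counted as non-events, and give it its own planning rate with a source.

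The cost is wording in the synopsis, section 5.3.2.2 and Table 9. Deaths and BPD status are already collected, and the sample size does not change. The downside is that deaths unrelated to the lung enter a respiratory composite; the supportive outcome and the separate death outcome let a reader see how much they contribute.
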